## 3.0 STUDY DESIGN

In this single-center pilot study, we will investigate possible short-term neurocognitive changes induced by deep brain stimulation (DBS) in patients with Parkinson’s disease between the “on” and off” state. During the “on” phase, bilateral monopolar stimulation of the electrode contact associated with the ventral STN will be turned on; testing in the “on” state will be tested at both theta (5-10 Hz) and gamma (100-180 Hz) stimulation. In order to improve blinding to “on” versus “off” states and increase the uniformity of stimulation parameters, the intensity will be adjusted to 2.5 V for all patients. Patients with baseline settings at less than 1.5 V will be excluded from the study. During the “off” phase, both DBS electrodes will be turned off. Since turning the stimulation “on” vs “off” may induce motor effects that could influence testing performance, we will examine if the order in which settings are applied impacts the results of cognitive testing.

During a single outpatient visit, a baseline assessment (baseline stimulation parameters, including frequency, pulse width and voltage) of each neuropsychological task will first be performed in order to accommodate patients to the given task and reduce practice effect. Patients will then perform a battery of tests with the stimulator “on” at the theta frequency, “on” at the gamma frequency, and off; the sequence of these three settings will be changed for each patient in a single-blind fashion. Thus, patients will complete this battery of tasks a total of four times. Duration of testing will be approximately three hours.

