#### **6.0 STRATIFICATION/DESCRIPTIVE FACTORS/RANDOMIZATION SCHEME**

The order of stimulation parameters after baseline will be changed for each patient by moving the order by one step. E.g. patient 1: gamma, theta off; patient 2: theta, off, gamma; patient 3: off, gamma theta. The subject will not be told which setting is being used.

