## Power analyses

Study	Projected Sample Size	Mean Result ± SD	Absolute Change (Percent Change)
RNGT	20	43±14	+8.6 (20%)
Delis Kaplan Executive Function	26	9.1±3.3	±1.8 (20%)
Verbal Fluency (preliminary data)	29	47±17	+9.4 (20%)
Quotient	Exploratory		

Non-parametric data analysis will be performed for each of the tasks, including RNGT, D-KEFS CWIT and the Quotient tasks. Each task will be analyzed using within-subjects ANOVA.

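### The plan names no session-position term in its ANOVA; run on setting alone, any remaining practice or fatigue trend would widen the standard errors of the setting contrasts

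*Combined protocol and SAP*

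**What the plan says.** Section 3.0 (Study Design) has a baseline run of each task, which "will first be performed in order to accommodate patients to the given task and reduce practice effect". Three further runs follow, under theta, gamma and off, so that "patients will complete this battery of tasks a total of four times" in one visit: "Duration of testing will be approximately three hours". The same section says that the effect of the order of settings on the test results will be examined, because switching stimulation may have motor effects. It does not say how.

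Section 6.0 sets the rotation: "The order of stimulation parameters after baseline will be changed for each patient by moving the order by one step". Its example is "patient 1: gamma, theta off; patient 2: theta, off, gamma; patient 3: off, gamma theta". With 30 patients this gives three orders of 10, and each setting falls equally often in each position.

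Section 13.0, under Power analyses, describes the analysis in two sentences: "Non-parametric data analysis will be performed for each of the tasks, including RNGT, D-KEFS CWIT and the Quotient tasks", and then "Each task will be analyzed using within-subjects ANOVA". It names no factors, neither setting nor position, and does not mention the order check.

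**The concern.** The baseline run is meant to reduce practice, not to abolish it, and a visit of about three hours can also tire patients. A net drift over the three rotated sessions is therefore plausible. The rotation protects the setting means against such a drift. It does not protect their standard errors unless the analysis takes position out of the residual.

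If the within-subjects ANOVA has setting as its only factor, differences between the first, second and third rotated sessions count as noise. Gamma against off (first aim) and theta against gamma (second aim) would then carry standard errors larger than the design warrants, and some of the power that the rotation makes available would be lost. If patients stop early and the three orders end up unequal, position would no longer be balanced over settings, and part of the drift would enter the setting means.

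**Working it through.** **Inputs.** From the documents: 30 patients, three orders, three rotated sessions, and the means, SDs and target changes in the power table. Assumed, because not stated: two-sided alpha 0.05, 80% power, tabled SD equal to the SD of within-patient differences, and a linear shift of *d* per session, in units of the within-patient residual SD *s*.

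**The plan's sample sizes.** n = (SD × (1.960 + 0.842) / change)²:

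- RNGT: (14 × 2.802 / 8.6)² = 20.8, so 21 (plan: 20)
- D-KEFS: (3.3 × 2.802 / 1.8)² = 26.4, so 27 (plan: 26)
- Verbal fluency: (17 × 2.802 / 9.4)² = 25.7, so 26 (plan: 29)

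The paired-t versions are 23, 29 and 28. No single variant tried gives all three rows, but a paired calculation comes close, and its largest value, 29, supports enrolling 30.

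**Error term.** There are 90 observations. Removing the mean, 29 df for patients and 2 for setting leaves 58. With position shifts −d, 0, +d and 10 patients per order, position is orthogonal to setting and its sum of squares is 30 × 2d² = 60d². Without a position term, the expected error mean square is s²(1 + 60d²/58) = s²(1 + 1.034d²) on 58 df. With the term it is s² on 56 df.

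**Standard error and power at N = 30.** The true SE of a contrast is s√(2/30) = 0.258s. The inflation ratio is √(1 + 1.034d²). Power is shown with / without position.

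| d | SE ratio | RNGT | D-KEFS | Verbal fluency |
|---|---|---|---|---|
| 0 | 1.00 | 91% / 91% | 84% / 84% | 85% / 85% |
| 0.25 | 1.03 | 91% / 90% | 84% / 82% | 85% / 83% |
| 0.5 | 1.12 | 91% / 87% | 84% / 77% | 85% / 78% |
| 1.0 | 1.43 | 91% / 69% | 84% / 56% | 85% / 57% |

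For scale: if 14 is the SD of RNGT differences, s = 14/√2 = 9.9, so d = 0.5 is about 5 RNGT points per session.

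**Simulation (6,000 trials per case).** The contrast is unbiased and its actual SD is about 0.26s at every d. Without position, the mean reported SE is 0.257s, 0.266s, 0.289s and 0.367s at d = 0, 0.25, 0.5 and 1.0, and the actual type I error is 4.6%, 4.3%, 3.2% and 0.7%. With position, the SE stays at about 0.257s and the error rate near 5%. Paired t-tests on two settings show much the same inflation (0.288s at d = 0.5).

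**Unequal orders.** The drift adds −2d to gamma minus off in the order gamma-theta-off, and +d in each of the other two orders.

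- One patient lost from gamma-theta-off (9, 10 and 10 complete): (−18 + 10 + 10)/29 = 0.07d
- Three lost from that order (7, 10 and 10): (−14 + 10 + 10)/27 = 0.22d

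At d = 0.5 these are about 0.03s and 0.11s, against an SE of about 0.26s.

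**The case against.** Four points can be made on the other side.

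**Silence is not exclusion.** A reader might infer that the plan has chosen a one-factor ANOVA and left position out. The text does not support that, because it names no factors at all. What stands is that the plan does not say whether position is modelled.

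**The order check may already cover it.** Position lies within the sequence-by-setting interaction. If the check in section 3.0 is run as that interaction in the same ANOVA, the trend leaves the error term (simulated SE 0.257s on 54 df). That is a natural reading, but the plan gives no method, and a check done apart from the main model would leave its error term as it was.

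**The trend may be small.** A full baseline battery comes first, and practice and fatigue may partly cancel. At d = 0.5 the drift from first to third rotated session is 1.0s, larger than the effects sought (for RNGT, 8.6/9.9 = 0.87s). At d = 0.25 the loss is only 1 to 2 points of power. This stands: the documents do not show that the standard errors will be too wide, only that they would be if a trend remains and is not modelled.

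**The analysis may be rank-based.** The error mean squares, degrees of freedom and power above hold for the parametric reading only. This also stands, and the plan must settle which reading applies.

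**Conclusion.** The point holds as a conditional one. If the ANOVA is fitted on setting alone and a session trend remains after baseline, the tests of both aims are conservative: the SE is about 3% too wide at d = 0.25, 12% at 0.5, and unchanged with no trend. These figures assume a linear trend, 10 complete patients per order and a parametric analysis; the power figures also rest on the assumed alpha and SD of differences.

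A reader might infer that the setting comparisons are biased or that false positives become more likely. With balanced orders neither follows: the estimates are unbiased and the type I error falls below its nominal level. Bias arises only if stops leave the orders unequal, and is small in the cases worked.

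For a single-center pilot this is a low-cost gain in precision and clarity, not a threat to validity. It is worth making because the term costs almost nothing when there is no trend.

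**What to change.** In section 13.0, state that for each score analysed by ANOVA the model for the three rotated sessions contains patient, setting and session position (first, second or third after baseline), with position as a categorical factor so that no trend shape is assumed. Estimate gamma minus off and theta minus gamma from that model. Leave the baseline run out of the comparison: it always comes first, so it cannot be separated from position.

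In the same edit, say how the order check in section 3.0 will be done and whether it is part of this model. Reconcile the non-parametric sentence with the ANOVA sentence; if ranks are used, apply the same position adjustment to the rank-based analysis.

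The cost is SAP wording and 2 of 58 error degrees of freedom, with about 0.1 point of power or less lost if there is no trend. No new data are needed, because the rotation already fixes each setting's position. The change does not deal with carryover: in this rotation, a setting that follows another always follows the same one, and a position term cannot separate that.

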## 16.0 ETHICAL AND REGULATORY CONSIDERATIONS

The study will be conducted in adherence to ICH Good Clinical Practice.

